2 STATISTICAL HYPOTHESES

For this single arm study, the analysis methods are estimation (for cumulative event rate of COWS increase ≥ 6 within the first 1, 6, 12, 24, and 48 hours) and description (COWS AUC within the first 1, 6, 12, 24, and 48 hours, and COWS and OC-VAS absolute scores and change from pre-treatment values at each timepoint). Therefore, statistical testing and hypotheses are not applicable.

2.1 Multiplicity Adjustment

There is no multiplicity adjustment.

3 SAMPLE SIZE DETERMINATION

Approximately 15 adult subjects with moderate to severe OUD are planned to be dosed with SUBLOCADE. Additional subjects may be enrolled to ensure that 15 subjects are dosed with SUBLOCADE and are evaluable for the key timepoints defined as 1, 6, 12, 24, and 48 hours post-SUBLOCADE (see [Section 5.3.1.](#))

With a sample size of 15, the probability to observe at least one case of precipitated withdrawal is 79.4%, assuming the true event rate is 10%, while the probability to observe at least one case of precipitated withdrawal is reduced to 53.7% if the true event rate is 5%.

[Table 5](#) provides the probabilities of observed events at different true event rates.

Table 5 Probabilities of Observed Events at Different True Event Rates

True Event Rate	0 event	At Least 1 Event	At Least 2 Events	At Least 3 Events
1%	0.860	0.140	0.010	0.0004
5%	0.463	0.537	0.171	0.036
8%	0.286	0.714	0.340	0.113
10%	0.206	0.794	0.451	0.184
15%	0.087	0.913	0.681	0.396
20%	0.035	0.965	0.832	0.602

4 POPULATIONS FOR ANALYSIS

Data for all subjects will be assessed to determine if they meet the criteria for inclusion in each analysis population prior to releasing the database and classifications will be documented per standard operating procedures.

Table 6 Populations for Analysis

Population	Description
Screened	All subjects who sign the informed consent document.
Enrolled	A subject will be considered enrolled if he/she receives at least 1 dose of TM BUP.

Full Analysis Set	The FAS population consists of all subjects who receive a SUBLOCADE injection and have data for at least 1 COWS assessment at the Pre-SUBLOCADE timepoint just before the SUBLOCADE injection and a COWS assessment for at least one of the scheduled timepoints within 48 hours after SUBLOCADE injection. The FAS will serve as the primary population for the analysis of key endpoints in this study.
Safety Analysis Set	The safety population will be used for the safety analysis, and it consists of all subjects who received at least 1 dose of SUBLOCADE. The safety population will serve as the primary population for the analysis of safety assessments related to SUBLOCADE.
TM BUP Analysis Set	The TM BUP Analysis Set consists of all subjects who received at least 1 dose of TM BUP. This analysis set will be used for analysis of the exploratory safety endpoint related to TM BUP. (Note: this is the same population as Enrolled).
PK Analysis Set	The PK Analysis Set will be used for the Exploratory PK endpoint analysis and will consist of all subjects who received the SUBLOCADE injection and have at least one NMP plasma concentration measurement post-SUBLOCADE. Subjects in the PK population with protocol deviations or events that impact the quality of the PK data will be assessed on a case-by-case basis.

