1. Upon arriving at the clinic, subjects will provide a urine sample for a UDS for qualitative and quantitative analysis, a urine sample for a pregnancy test (child-bearing females only), perform an alcohol breathalyser test and self-report their concomitant medications since screening and recent illicit drug use (including the use of a TimeLine Follow Back [TLFB]). If subject is deemed eligible for check-in the subject will then be assessed for withdrawal symptoms using COWS and for craving using OC-VAS.
 2. Details subjects illicit drug use, in addition to report question capturing frequency, route and date of last use.
 3. Required for female subjects of childbearing potential only.
 4. Per Investigator's discretion, subjects with positive test may either remain in the clinic or be re-scheduled to return on another date.
 5. Per Investigator's discretion, subjects with COWS <8 may either remain in the clinic and repeat assessments at a later time or be re-scheduled to return on another date. The COWS may be repeated at any time, per Investigator's discretion, and should always be repeated just before TM-BUP and SUBLOCADE administration. The OC-VAS should be performed each time a COWS assessment is performed.
 6. If the subject is asleep at 16 and 20 hours, the assessments will not be performed, and the reason should be noted in the CRF.
 7. Includes a review of any previous (taken since screening) and ongoing medications (including over-the-counter) and herbal supplements.
 8. Includes systolic and diastolic blood pressure, pulse rate, respiratory rate and oral temperature after the subject has been in a sitting position for ≥ 3 minutes.
 9. An ECG will be collected after the subject has been in a supine position for ≥ 5 minutes.
 10. Eligible subjects must meet the buprenorphine dosing criterion, prior to receiving 4mg TM buprenorphine.
 11. A sub-set of serum chemistry to be performed including: ALP, ALT, AST, bilirubin, albumin, total protein, GGT and LD only. For increased LFTs, subject should be asked to return to the clinic for weekly repeat liver chemistry testing (ALP, ALT, AST, and total bilirubin) until resolved, stabilised or return to within baseline values, per Section 8.2.7.3.
 12. Weight to be captured; BMI will be calculated in the database using height from screening.
 13. Assessment to be performed anytime pre-SUBLOCADE dose.
 14. Eligible subjects meet SUBLOCADE dosing criteria, prior to receiving SUBLOCADE.

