The number and percentage of subjects with ≥ 6 -point increase in COWS within the first 6, 12, 24, or 48 hours post SUBLOCADE administration will be summarized using the FAS. As this is a cumulative endpoint, once a subject has a ≥ 6 -point increase in COWS, the subject will be counted for that timepoint and all subsequent timepoints. The denominator at each timepoint will be the number of subjects who have a pre-SUBLOCADE COWS assessment and either 1) have a ≥ 6 -point increase in COWS at or before the timepoint, or 2) have at least one post-SUBLOCADE COWS assessment within the timepoint interval. COWS assessments occurring at unscheduled visits will be included in the derivation.

The AUC will be calculated using the linear trapezoidal method, i.e.,

$$AUC = \frac{1}{2} \sum_{i=0}^n (T_{i+1} - T_i)(C_{i+1} - C_i)$$

where T_i is the i^{th} time value, C_i is the i^{th} COWS score, and n is the number of time values. Inherent to this formula, missing COWS scores are imputed in a linear manner.

The area under the curve (AUC) of COWS score from the time of administration of SUBLOCADE (i.e., time 0) through 6, 12, 24 and 48 hours after SUBLOCADE administration will be calculated using the FAS, and summarized using descriptive statistics for continuous endpoints (e.g., n, mean, median, SD, minimum and maximum).

The total score on the COWS and opioid craving visual analogue scale (OC-VAS) during the treatment period (i.e. at each assessment timepoint from administration of TM buprenorphine at Day 1 through EOT) will be summarized using descriptive statistics for continuous endpoints for the absolute value and change from the pre-TM Buprenorphine and pre-SUBLOCADE values. The analysis will use the FAS and observed data.

14.4.2 *Exploratory Endpoints*

The number and percentage of subjects who experience precipitated withdrawal from TM buprenorphine (defined as an increase in COWS by ≥ 6 from prior to the most recent dose of TM buprenorphine before SUBLOCADE administration) will be summarized using the TM Buprenorphine analysis set. The number, percentage and its 2-sided 95% exact CI using binomial distribution (Clopper-Pearson method) will be constructed using observed data.

Peak and overall plasma exposure to NMP following a single SC injection of 300 mg SUBLOCADE will be evaluated. The following PK parameters for NMP will be derived by non-compartmental analysis:

- C_{\max} : maximum observed plasma concentration

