5.3 Key Endpoints Analysis

The analysis of key endpoints will be performed using the FAS, unless otherwise specified. The derived endpoints will be listed for the FAS.

The key timepoints for the analysis are defined as 1, 6, 12, 24, and 48 hours post-SUBLOCADE.

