5.3.2 COWS Total Score Increase by ≥ 6 - Main Analytical Approach

The cumulative event rate for COWS Total Score increase by ≥ 6 from the pre-SUBLOCADE value will be estimated via the Kaplan-Meier method (1958), using the 5 key timepoints, 1, 6, 12, 24 and 48 hours after SUBLOCADE administration (i.e., time=0). Note that for the 1-hour key timepoint the event is referred to as precipitated withdrawal. A subject will be considered in the risk evaluation set at a specific key timepoint if the subject had a pre-SUBLOCADE COWS assessment and either 1) an increase in COWS by ≥ 6 from the pre-SUBLOCADE value within the current time interval (from the previous key timepoint to the current key timepoint), or 2) had a COWS assessment at the current key timepoint and all the prior key timepoints. If a subject has missing COWS assessment at one or more above key timepoints (1, 6, 12, 24 and 48 hours after SUBLOCADE administration), the subject is censored at the last key timepoint prior to the first missing timepoint.

The values for the event occurrence, time, and censoring parameters are assigned sequentially for the subject disposition events according to the order and criteria in Table 7.

Table 7 Parameters for Kaplan-Meier Method

Order of assignment	Disposition Event	Event of COWS Total Score Increase by ≥ 6	Time (hours)	Censored
1	An increase in COWS total score by ≥ 6 from the pre-SUBLOCADE value at any timepoint (scheduled or unscheduled) within 48 hours after SUBLOCADE injection	Yes	Nominal time of the first key timepoint on or after the COWS assessment meeting an increase in COWS total score by ≥ 6 from the pre-SUBLOCADE value	No
2	Missing COWS assessment at a key timepoint and without an increase in COWS total score by ≥ 6 from the pre-SUBLOCADE value within 48 hours	No	Nominal time of last key timepoint prior to the first missing key timepoint (i.e., 0, 1, 6, 12 or 24)	Yes
3	Completed COWS assessment at 1, 6, 12, 24, and 48 hours and without an increase in COWS total score by ≥ 6 from the pre-SUBLOCADE value within 48 hours	No	48	Yes

A Kaplan-Meier plot of the cumulative event rate from time=0 to 48 hours will be produced.

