6.3 Appendix 3: Definition and Use of Visit Windows in Reporting

Nominal visits will be used for the analysis without regard to visit windows.

The mapping of the protocol/CRF visits to the analysis visits will be implemented as follows in Table 11. Unscheduled visits will be given an analysis visit number in sequential order according to chronological date/time following the most recent scheduled visit.

Table 11 Visit Mappings for Analysis

Protocol/CRF Visit number (VISITNUM)	Protocol/CRF VISIT (VISIT)	Planned time point number/hour (--TPTNUM)	Planned timepoint name /Hour (-TPT)	Analysis Visit Number (AVISITN)	Analysis Visit (AVISIT)	Analysis Timepoint Number (ATPT)	Analysis Timepoint (ATPT)
1	Screening (-30 to -1)	.		1	Screening		
	Unscheduled ¹			1.1	Day 1 (Check-in) ¹		
	Unscheduled ¹			1.2	Pre-First TM BUP ¹		
	Unscheduled ¹			1.3	Post-First TM BUP ¹		
2	Day 1 (Check-in)	.		2	Day 1 (Check-in)		
3	Pre-TM BUP	.		3	Pre-TM BUP		
5	Pre-Sublocade	.		5	Pre-Sublocade		
7	Post-Sublocade	1	1 Hour Post Sublocade Dose	7	Post-Sublocade	1	1 Hour

Protocol/CRF Visit number (VISITNUM)	Protocol/CRF VISIT (VISIT)	Planned time point number/hour (-TPTNUM)	Planned timepoint name /Hour (-TPT)	Analysis Visit Number (AVISITN)	Analysis Visit (AVISIT)	Analysis Timepoint Number (ATPT)	Analysis Timepoint (ATPT)
7	Post-Sublocade	2	2 Hours Post Sublocade Dose	7	Post- Sublocade	2	2 Hours
7	Post-Sublocade	3	3 Hours Post Sublocade Dose	7	Post- Sublocade	3	3 Hours
7	Post-Sublocade	4	4 Hours Post Sublocade Dose	7	Post- Sublocade	4	4 Hours
7	Post-Sublocade	6	6 Hours Post Sublocade Dose	7	Post- Sublocade	6	6 Hours
7	Post-Sublocade	8	8 Hours Post Sublocade Dose	7	Post- Sublocade	8	8 Hours
7	Post-Sublocade	12	12 Hours Post Sublocade Dose	7	Post- Sublocade	12	12 Hours
7	Post-Sublocade	16	16 Hours Post Sublocade Dose	7	Post- Sublocade	16	16 Hours
7	Post-Sublocade	20	20 Hours Post Sublocade Dose	7	Post- Sublocade	20	20 Hours
8	Day 2	24	24 Hours Post Sublocade Dose	8	Day 2	24	24 Hours
8	Day 2	30	30 Hours Post Sublocade Dose	8	Day 2	30	30 Hours

Protocol/CRF Visit number (VISITNUM)	Protocol/CRF VISIT (VISIT)	Planned time point number/hour (-TPTNUM)	Planned timepoint name /Hour (-TPT)	Analysis Visit Number (AVISITN)	Analysis Visit (AVISIT)	Analysis Timepoint Number (ATPT)	Analysis Timepoint (ATPT)
8	Day 2	36	36 Hours Post Sublocade Dose	8	Day 2	36	36 Hours
9	Day 3	48	48 Hours Post Sublocade Dose	9	Day 3	48	48 Hours
10	Day 8	.		10	Day 8		
11	Day 15	.		11	Day 15		
12	Day 22	.		12	Day 22		

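### An injected subject with no scheduled COWS in the 48 hours after injection is outside the FAS, even if an unscheduled COWS shows the key event

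*SAP*

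**What the plan says.** **Who is analysed.** SAP Section 4, Table 6, sets three conditions for the FAS: a SUBLOCADE injection, a COWS at the pre-SUBLOCADE timepoint, and "a COWS assessment for at least one of the scheduled timepoints within 48 hours after SUBLOCADE injection". SAP 5.3 then states: "The analysis of key endpoints will be performed using the FAS, unless otherwise specified". SAP 5.3.2 specifies no other set for the event rate.

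**What counts as an event.** The first row of SAP Table 7 takes a rise of 6 or more from the pre-SUBLOCADE value "at any timepoint (scheduled or unscheduled) within 48 hours after SUBLOCADE injection". Values are "assigned sequentially for the subject disposition events according to the order and criteria in Table 7", so the event row is applied before the row that censors for a missing key timepoint. The risk-set rule in the text of 5.3.2 likewise asks an event subject only for a pre-SUBLOCADE COWS and the event. Protocol 14.4.1 agrees on the source of events: "COWS assessments occurring at unscheduled visits will be included in the derivation".

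**When COWS is taken.** SAP Tables 4 and 11 schedule 13 post-injection assessments, from 1 hour to the one labelled "48 Hours Post Sublocade Dose". Two of them may be omitted by design: "If the subject is asleep at 16 and 20 hours, the assessments will not be performed". Extra assessments are foreseen. A footnote to the COWS row of Protocol Table 2 says "The COWS may be repeated at any time" at the Investigator's discretion, and Protocol Section 8 allows any assessment to be done more often if clinically indicated.

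**The concern.** The entry rule for the analysis set is narrower than the event rule applied within it. The subject at risk of falling between them deteriorates soon after injection, is scored at once outside the schedule, and then refuses further scoring or leaves. That would be rapid precipitated withdrawal, which the study is meant to detect. Exclusion would then be a consequence of the outcome, and it would act on a key safety endpoint in a study of about 15 subjects, where one event decides whether the result reads as one case or none.

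**Working it through.** **1. The plan's own figure.** With n = 15 and a true rate of 10%, P(at least one event) = 1 − 0.90^15 = 0.794; at 5% it is 1 − 0.95^15 = 0.537. Both match SAP Table 5. The point does not rest on these figures, but they show a design that turns on whether any event is seen.

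**2. Apply the two rules.** Take an injected subject with a pre-SUBLOCADE COWS.

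| Post-injection COWS | Rise ≥6? | In FAS (Table 6)? | Table 7 result if analysed | Effect of requiring a scheduled COWS |
|---|---|---|---|---|
| At least one scheduled, plus unscheduled | Yes, on the unscheduled only | Yes | Event, at the next key timepoint | None |
| Unscheduled only | No | No | Censored at time 0 (second row) | None: never at risk at a key timepoint |
| Unscheduled only | Yes | No | Event (first row) | Event and subject removed from the key rate |

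Among subjects with no scheduled COWS, the requirement changes the Kaplan-Meier estimate only in the last line, and there it can only remove an event.

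**3. Size, if it happens once.** Assume 15 injected, one such subject, whose event is assigned to the 1-hour key timepoint, and no other censoring. The Kaplan-Meier estimate is then the simple proportion. SAP 5.3.2 specifies no interval for this rate; the exact (Clopper-Pearson) 95% limits below are only for scale.

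| Scenario | Counted | Excluded (current text) |
|---|---|---|
| No other event, no replacement | 1/15 = 6.7% (0.2% to 31.9%) | 0/14 = 0% (0% to 23.2%) |
| One other event, no replacement | 2/15 = 13.3% (1.7% to 40.5%) | 1/14 = 7.1% (0.2% to 33.9%) |
| No other event, one replacement enrolled | 1/16 = 6.3% (0.2% to 30.2%) | 0/15 = 0% (0% to 21.8%) |

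The third line is included because SAP Section 3 allows extra subjects to be enrolled to reach 15 evaluable.

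**4. How likely.** The documents give no missingness rate. As an assumption, let each of the 13 assessments be missing independently with probability q. One subject misses all of them with probability q^13, and at least one of 15 does so with probability 1 − (1 − q^13)^15.

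| q | One subject | At least one of 15 |
|---|---|---|
| 0.3 | 0.00000016 | 0.0002% |
| 0.5 | 0.00012 | 0.18% |
| 0.7 | 0.0097 | 13.6% |

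These figures concern missing every scheduled COWS; the case also needs an unscheduled event. On the other side, independence is doubtful. A subject who leaves or refuses misses the remaining assessments together, and SAP 1.1 itself raises the possibility that COWS were missing for informative reasons. The table shows only that scattered gaps would hardly ever produce the case; early departure or refusal would have to.

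**The case against.** The strongest reply is that the gap is very small. A reader might infer that any withdrawal caught only on an unscheduled COWS is lost. The documents do not support that: the FAS does not ask for the event to fall on a scheduled assessment, and a single scheduled COWS among 13, with or without a rise, keeps the subject in. Subjects are also due to stay in the clinic for about 48 hours, and SAP 6.3 analyses nominal visits without applying windows, so an early score entered under the 1-hour visit would qualify. The SAP's remarks on missing COWS show gaps; they do not show that any subject lacks all 13. All of this stands, and it makes the case rare.

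A reader might also infer that the event vanishes from the report. It does not. The subject stays in the Safety Analysis Set and the adverse event summaries, including those for the first 48 hours (SAP 5.5.2), although withdrawal appears there only if recorded as an adverse event. The individual COWS plots (5.3.9) and the COWS and adverse event listing (5.5.2) remain, and the adjudication committee reviews enrolled subjects, not just the FAS (5.3.3.2). This stands too, but adjudication is a sensitivity analysis based on clinical judgement and its denominator is not stated. None of these outputs corrects the main event rate or its plot.

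Finally, the SAP did not tighten the set. Protocol 14.3.1 asked for COWS assessments for 48 hours, and the SAP relaxed this to one scheduled COWS. That is a fair account of the direction of change, but the remaining mismatch with Table 7 is still there.

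**Conclusion.** The point holds in a narrow form. An injected subject with a pre-SUBLOCADE COWS, none of the 13 scheduled COWS within 48 hours, and a rise of 6 or more on an unscheduled COWS only is excluded from the FAS, although SAP Table 7 and the event derivation in Protocol 14.4.1 would count the event. If one such subject exists, the main rate is biased low, by 6.7 percentage points without replacement (1/15 to 0/14) or 6.3 with one replacement (1/16 to 0/15), given no other event or censoring. If none exists, the estimate is unaffected. It would be wrong to say that the rate is biased as things stand, because the documents report no such subject and give no basis for a frequency. The case for acting is that the restriction can move this estimate in one direction only, depends on the outcome, and gains nothing for the event analysis.

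**What to change.** In SAP Table 6, define the FAS as all injected subjects with a pre-SUBLOCADE COWS and any COWS assessment, scheduled or unscheduled, within 48 hours after the injection. This matches the first row of Table 7. Add the change of FAS definition to SAP 6.2, which does not currently list the FAS among the departures from the protocol.

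The cost is one phrase and one line in the appendix, with no new data. If no subject is affected, the Kaplan-Meier estimate stays the same. A subject admitted by the change without an event would be censored at time 0. The FAS demographic and drug-use tables would gain any such subject, and the COWS AUC could too if the unscheduled score falls late enough for an interval. The change should be made before the population classifications are fixed, which SAP Section 4 places ahead of database release.

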5 STATISTICAL ANALYSES

5.1 General Considerations

5.1.1 Statistical Analyses and Coding

Statistical analyses will be performed using version 9.4 (or higher) of SAS.

The non-compartmental PK analysis of NMP data will be performed using Phoenix WinNonlin version 8.1 or higher (Certara, Princeton, NJ).

The AEs and medical/psychiatric history will be coded using the latest version of MedDRA available at the time of database lock.

The concomitant medications will be coded using the latest version of the World Health Organization (WHO) Drug Dictionary.

The final analysis will occur after the database lock.

5.1.2 Treatment Labels

The treatment labels will be presented in the tables, listings and figures (TLFs) as either

SUBLOCADE 300mg, or

TM Buprenorphine only or TM BUP only

as applicable to the analysis population being presented.

5.1.3 Definition of Pre-TM BUP Value, Pre-SUBLOCADE Value, and Pre-SUBLOCADE Baseline

For analyses of COWS and OC-VAS (i.e., the key and exploratory endpoints), the Pre-TM BUP value is the measure obtained at the Pre-TM BUP timepoint just before a TM-BUP dose for induction, and the Pre-SUBLOCADE value is the measure obtained at the Pre-SUBLOCADE timepoint just before the SUBLOCADE injection.

For the analysis of other safety assessments (described in Section 5.5), the Pre-SUBLOCADE baseline will be the last non-missing value prior to the administration of SUBLOCADE.

5.1.4 Definition of Analysis Phases

Screening phase: starts from the date of screening visit and ends at the date/time of the first TM-BUP dose for induction.

Induction phase: starts from the date/time of the first TM-BUP dose for induction and ends at the date/time of SUBLOCADE injection or TM-BUP ET visit.

SUBLOCADE treatment phase: starts from the date/time of SUBLOCADE injection through the date of last visit in the study (EOT or EOS, whichever is applicable).

The overall treatment period for the study is the combination of induction and SUBLOCADE treatment phases.

5.1.5 General Conventions for Analysis

If the FAS and safety analysis sets comprise the same set of subjects, analyses indicated to be performed on both populations will be performed only on the FAS population.

Continuous variables will be summarised using the descriptive statistics mean, standard deviations (SD), median, minimum and maximum, unless other statistics are specified. Categorical variables will be reported as frequency counts (including number missing) and the percentage of subjects in corresponding categories.

Individual subject data will be presented by subject in data listings. Data listings will include all data collected from the initial screening visit to the EOS (including unscheduled visits), i.e., for the Screened Population unless otherwise specified.

Figures presenting summary data will include scheduled visits and assessments only. Figures of individual subject data will include all visits, scheduled and unscheduled. Visits will be presented chronologically.

Observed data is used for analysis, unless handling of missing data is described otherwise within the analysis description or in [Section 6.5](#).

